4.3.3 Treatment of Nivolumab or Ipilimumab-related infusion reactions

Since both nivolumab and ipilimumab contain only human immunoglobulin protein sequences, it is unlikely to be immunogenic and induce infusion or hypersensitivity reactions. However, if such a reaction were to occur, it might manifest with fever, chills, rigors, headache, rash, pruritus, arthralgias, hypotension, hypertension, bronchospasm, or other allergic-like reactions.

Treatment recommendations are provided below and may be modified based on local treatment standards and guidelines, as appropriate:

NCI CTCAE Grade	Treatment	Premedication at subsequent dosing
Grade 1 Mild reaction; infusion interruption not indicated; intervention not indicated	Remain at bedside and monitor subject until recovery from symptoms.	The following prophylactic pre-medications are recommended for future infusions: 
 • Diphenhydramine 50 mg (or equivalent) and/or • Acetaminophen 325 to 1000 mg at least 30 minutes before additional nivolumab or ipilimumab administrations
Grade 2 Moderate reaction requires therapy or infusion interruption but responds promptly to symptomatic treatment [eg, antihistamines, non-steroidal anti- inflammatory drugs, narcotics, corticosteroids, bronchodilators, IV fluids]; prophylactic medications indicated for < 24 hours	Stop the nivolumab/ipilimumab infusion, begin an IV infusion of normal saline, and treat the subject with diphenhydramine 50 mg IV (or equivalent) and/or acetaminophen 325 to 1000 mg; Remain at bedside and monitor subject until resolution of symptoms. Corticosteroid and/or bronchodilator therapy may also be administered as appropriate. If the infusion is interrupted, then restart the infusion at 50% of the original infusion rate when symptoms resolve; if no further complications ensue after 30 minutes, the rate may be increased to 100% of the original infusion rate. Monitor subject closely. If symptoms recur, then no further nivolumab will be administered at that visit.	For future infusions, the following prophylactic pre-medications are recommended: 
 • Diphenhydramine 50 mg (or equivalent) and/or • Acetaminophen 325 to 1000 mg should be administered at least 30 minutes before nivolumab or ipilimumab infusions. If necessary, corticosteroids (up to 25 mg of SoluCortef or equivalent) may be used.
Grades 3 or 4 Severe reaction, Grade 3: prolonged [ie, not rapidly responsive to symptomatic medication and/or brief interruption of infusion]; recurrence of symptoms following initial improvement; hospitalization indicated for other clinical sequelae [eg, renal impairment, pulmonary infiltrates]. Grade 4: Life-threatening; pressor or ventilatory support indicated	Immediately discontinue infusion of nivolumab/ipilimumab infusion. Begin an IV infusion of normal saline and treat the subject as follows: Recommend bronchodilators, epinephrine 0.2 to 1 mg of a 1:1000 solution for subcutaneous administration or 0.1 to 0.25 mg of a 1:10,000 solution injected slowly for IV administration, and/or diphenhydramine 50 mg IV with methylprednisolone 100 mg IV (or equivalent), as needed.	No subsequent dosing

NCI CTCAE Grade	Treatment	Premedication at subsequent dosing
	
Subject should be monitored until the Investigator is comfortable that the symptoms will not recur. Nivolumab or ipilimumab will be permanently discontinued. Investigators should follow their institutional guidelines for the treatment of anaphylaxis. Remain at bedside and monitor subject until recovery of the symptoms
 
In case of late-occurring hypersensitivity symptoms (eg, appearance of a localized or generalized pruritus within 1 week after treatment), symptomatic treatment may be given (eg, oral antihistamine or corticosteroids)
	

4.4 Treatment with ipilimumab and or nivolumab beyond progression

In the event of an initial assessment of PD (based on RECIST Version 1.1), a subject may continue to receive the assigned study treatment as long as none of the criteria listed below are met.

- a. Confirmed PD: a subsequent scan obtained no sooner than 4 weeks from prior scan is suggestive of PD by RECIST 1.1 (see section 6.6), and the patient has clinical decline. NOTE: If PD is confirmed but the patient continues to have clinical benefit (e.g. improvement of symptoms and is tolerating treatment), the patient can continue treatment beyond PD per clinician's discretion.
- b. Meets any of the other investigational product discontinuation criteria (Section 4.3.2)
- c. Clinical symptoms or signs indicating significant PD, for example the benefit-risk ratio of continuing therapy is no longer justified.
- d. Decline in ECOG performance status.
- e. Threat to vital organs/critical anatomical sites (e.g., spinal cord compression) requiring urgent alternative medical intervention, and continuation of study therapy would prevent institution of such intervention.

If the lesions included in the tumor burden subsequently regress to the extent that the criteria for PD are no longer met, then treatment may continue according to the treatment schedule.

4.5 Interim Safety Analyses

Enrollment will be paused for a safety analysis after the first 15 evaluable ACC patients have been enrolled and treated. If ≥ 7 patients have been discontinued after <24 weeks of treatment for any reason (including toxicity, progression, intolerance etc.) accrual of ACC patients will be terminated. Otherwise, the study may continue enrollment until a total of up to 43 ACC subjects are treated.

An additional 20 patients with non-ACC MSGT's will be treated as an exploratory cohort. They can be enrolled at any point throughout the study and will not count toward the 15-patient safety analysis. A separate safety analysis will take place to analyze the first 10 non-ACC patients who are enrolled and treated. If >2 patients discontinue treatment prior

NU Study Number: NU 16N03
BMS Study Number: CA 209-802

to 24 weeks (for reasons other than withdrawal of consent), accrual of non-ACC patients will discontinue.

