Up to 43 patients will be enrolled with metastatic/recurrent ACC of any site of origin with evidence of disease progression who are not candidates for curative surgical or radiation therapy. An exploratory cohort of 20 patients with non-ACC of major or minor salivary glands will be enrolled concurrently.

**The first 15 ACC patients will be assessed for safety, and ACC accrual will be terminated if ≥ 7 patients are withdrawn after <24 weeks of treatment for any reason other than withdrawal of consent. Otherwise, enrollment will continue for a total of 43 ACC patients. The exploratory cohort of 20 non-ACC MSGT's will follow an independent accrual process to ACC and will also be assessed for safety; if >2 of the first 10 non-ACC patients are withdrawn after <24 weeks of treatment, the non-ACC cohort will be closed to accrual.

[figure not shown]

NU Study Number: NU 16N03
BMS Study Number: CA 209-802

STUDY SUMMARY

Title	Phase II study of nivolumab and ipilimumab for treatment of metastatic/recurrent adenoid cystic carcinoma of all anatomic sites of origin and non-adenoid cystic carcinoma malignant tumors of the salivary gland
Version	October 6, 2022, Amendment 8
Study Design	Simon two-stage single arm multi-center phase II clinical trial
Study Center(s)	Northwestern University
Objectives	
Primary:
 
 (1) To assess median progression-free survival (PFS) as well as PFS at 6 and 12 months in patients with recurrent or metastatic adenoid cystic carcinoma treated with a combination of nivolumab and ipilimumab. 
Secondary:
 
 (1) To assess the efficacy of nivolumab and ipilimumab according to response rate (RR), disease control rate (DCR) or clinical benefit rate (CBR) at 6 and 12 months- defined as sum of CR, PR, and SD, overall survival (OS) and progression free survival (PFS) in the above population using RECIST criteria. (2) To assess the efficacy of nivolumab and ipilimumab according to ORR, DCR, PFS, and OS in the above population using immune-related RECIST (irRECIST) criteria. (3) To assess the safety and tolerability profile of nivolumab and ipilimumab therapy in the above population using CTCAE version 4.03 
Exploratory:
 
 (1) To assess the immune-related biomarkers and their association with treatment response (2) To assess activity of nivolumab and ipilimumab in non-ACC malignant salivary gland tumors (MSGTs) using OS, PFS, CBR, and ORR

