3.0 PATIENT ELIGIBILITY

The target population for this study is patients with metastatic/recurrent adenoid cystic carcinoma (ACC) and non-adenoid cystic carcinomas (non-ACC) of major or minor salivary glands who are not surgical or radiation candidates with evidence of disease progression. This study will be led by Northwestern University. At Northwestern University, there is no competing trial.

A total of 63 [43 patients with ACC plus 20 patients with non-ACC MSGT (exploratory group)] subjects will be needed for this trial. Approximately 2 potentially eligible patients are seen per month, and it is anticipated that at least 2 per month will be accrued. Potential patients may be referred to the Principal Investigator (PI) at Northwestern University.

Eligibility will be evaluated by the study team according to the following criteria. Eligibility waivers are not permitted. Subjects must meet all of the inclusion and none of the exclusion criteria to be registered to the study. Study treatment may not begin until a subject is registered. Please refer to Section 11 for complete instructions regarding registration procedures.

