6.8 Evaluable patients

All patients who receive at least one dose of nivolumab will be considered evaluable for the toxicity endpoints.

All patients who receive at least one dose of nivolumab and have a radiologic evaluation of disease are evaluable for efficacy endpoints.

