10.2 Sample Size and Accrual

A Simon two stage optimum Phase II design will be used ⁴⁶. The main outcome is median Progression Free Survival (PFS) as well as PFS at 6 and 12 months. The optimal two-stage design to test the null hypothesis that $P \leq 0.450$ versus the alternative that $P \geq 0.650$ has an expected sample size of 24.70 and a probability of early termination of 0.654. If the drug is actually not effective, there is a 0.048 probability of concluding that it is (the target for this value was 0.050). If the drug is actually effective, there is a 0.196 probability of concluding that it is not (the target for this value was 0.200). After testing the drug on 15 patients in the first stage, ACC accrual will be terminated if 7 or more patients are withdrawn from the study after <24 weeks of treatment for any reason other than withdrawal of consent (this includes toxicity, PD, intolerance etc.) If the trial goes on to the second stage, a total of 43 patients will be studied. If the total number responding (defined as stable disease or better) is less than or equal to 24, the drug is rejected. An exploratory group of 20 patients with MSGTs will be included in the study, in addition to the 43 patients mentioned above. They can be enrolled in any order within the total accrual of 63 patients and will not participate in statistical analysis. A separate safety analysis will take place; if >2 of the first 10 non-ACC patients are withdrawn after <24 weeks of treatment, non-ACC accrual will discontinue.

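### Section 4.5 does not require 24 weeks of follow-up before the ACC stage-1 count, sets no condition for ending the pause, and leaves *evaluable* undefined for this look

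*Combined protocol and SAP*

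**What the plan says.** Section 4.5 (Interim Safety Analyses) is the only place that times the ACC look: "Enrollment will be paused for a safety analysis after the first 15 evaluable ACC patients have been enrolled and treated". ACC accrual ends if 7 or more of them have been discontinued with less than 24 weeks of treatment; otherwise enrollment may go on to 43. No minimum follow-up is given, and no length or release condition for the pause.

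The Study Schema says only "The first 15 ACC patients will be assessed for safety". The Summary and 10.2 likewise refer to 15 patients in the first stage. None of the three uses the word *evaluable* or adds any timing. Within 4.5, the parallel look at the first 10 non-ACC patients also omits the word.

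Section 6.8 gives two senses of evaluable. For toxicity, one dose of nivolumab is enough. For efficacy: "All patients who receive at least one dose of nivolumab and have a radiologic evaluation of disease are evaluable for efficacy endpoints". Section 6.4 draws the same distinction.

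Section 10.2 makes this look stage 1 of a Simon optimal design that "has an expected sample size of 24.70 and a probability of early termination of 0.654". On accrual, section 3.0 says "it is anticipated that at least 2 per month will be accrued", for both cohorts together.

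**The concern.** The outcome counted takes 24 weeks to observe, but the trigger is enrollment and treatment of 15 patients. Followed literally, a patient in week 3 counts as a non-failure, and accrual can resume on a count that is low only because it is immature. The look exists to limit how many patients receive an inactive or intolerable regimen, and that protection would be weakened.

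The undefined word adds a second uncertainty. In the efficacy sense, a patient who stops or dies before the first 12-week scan leaves the set of 15, although that patient is a failure the rule is meant to count. Two teams following 4.5 in good faith could count different patients at different times and decide differently.

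**Working it through.** **Inputs.** From 10.2: p0 = 0.45, p1 = 0.65, n1 = 15, n = 43, drug rejected at 24 or fewer successes. From 4.5 and 10.2: stop at 7 or more failures, that is, 8 or fewer successes. From 3.0: at least 2 patients a month over both cohorts; an even split gives 2 × 43/63 = 1.37 ACC patients a month. Failure times, ACC accrual share and early-leaver rates are not in the documents and are assumptions here.

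**1. The plan's own figures.** With a stage-1 stop at 7 or fewer successes (8 or more failures), P(Bin(15, 0.45) ≤ 7) = 0.654. Expected sample size is 15 + (1 − 0.6535) × 28 = 24.70, type I error 0.048 and type II error 0.196. All stated values reproduce, but they belong to a cut-off of 8 failures, not the written 7. That mismatch is a separate matter, so both cut-offs are shown below.

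**2. Full 24-week follow-up, written cut-off.** P(Bin(15, 0.55) ≥ 7) = 0.818.

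**3. Count taken w weeks after patient 15's first dose.** Assume a constant hazard with 55% failing by week 24: λ = −ln(0.45)/24 = 0.0333 per week. A patient followed for t weeks (t ≤ 24) has been seen to fail with probability 1 − exp(−λt). At t = 3 this is 0.095, against 0.55 in the end. Simulation with Poisson accrual gives, for an inactive drug:

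| ACC patients/month | Wait w | Mean number of 15 with 24 weeks since first dose | P(stop), ≥7 | P(stop), ≥8 |
|---|---|---|---|---|
| 1 | 0 | 8.5 | 0.47 | 0.28 |
| 1.37 | 0 | 6.5 | 0.37 | 0.20 |
| 2 | 0 | 3.3 | 0.23 | 0.11 |
| 1 to 2 | 12 weeks | 11.2 to 8.5 | 0.74 to 0.69 | 0.55 to 0.49 |
| any | 24 weeks | 15 | 0.82 | 0.654 |

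Evenly spaced accrual gives 0.53, 0.42 and 0.24 for the immediate look at ≥7. Other failure-time patterns at 2 a month, also with even accrual, are lower: 0.17 if failures are linear in time, 0.15 if all fall at the week-12 scan, and 0.01 if half fall at week 12 and half at week 24.

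**4. Expected sample size.** EN = 43 − 28 × P(stop). For the immediate look at 2 a month, the unrounded stop probabilities of 0.228 and 0.106 give 36.6 (≥7) and 40.0 (≥8).

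**5. Type I error.** If the look never stopped the trial, P(Bin(43, 0.45) ≥ 25) = 0.058. That is the ceiling with all 43 in the final count.

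**6. Efficacy sense of evaluable, full follow-up.** If a share u leaves before any re-scan and is dropped, the failure rate among those counted is (0.55 − u)/(1 − u). For u = 0.10, 0.15 and 0.20 this is 0.50, 0.471 and 0.438, and P(stop) at ≥7 is 0.70, 0.61 and 0.51.

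**The case against.** The strongest reply is that 4.5 does not order an immature look. It pauses enrollment, which leaves room for the 15 to mature, and 10.2 presents the look as Simon stage 1, where first-stage outcomes are ordinarily known. A 24-week wait loses nothing. This stands: a reader might infer that the protocol requires the count without follow-up, and the text does not say so. But it does not require waiting either, and a pause with no release condition does not supply the requirement.

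A reader might also infer that early leavers are excluded. The documents point the other way. The section calls this a safety analysis, and the toxicity sense in 6.4 and 6.8 keeps everyone dosed. The efficacy sense remains possible because the count includes progression and serves as stage 1, but it is the less likely reading.

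It can be said that a 12-week wait (0.69 to 0.74) still exceeds the stated 0.654. That mixes cut-offs: 0.654 belongs to 8 failures, where a 12-week wait gives 0.49 to 0.55.

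Two further limits stand. The final rule is untouched, so a much higher false-positive risk should not be inferred; an early look also stops an effective drug less often. And this is not the only accrual stop in the text: 8.1.11 and 8.2.11 say enrollment stops after 12 treated participants if no tumor shrinks. Those sentences look like template remnants (8.2.11 names anal cancer), but they are current text. The plan also provides for high-intensity monitoring and committee review of adverse events.

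**Conclusion.** The point holds as a gap in the rule. Section 4.5 sets neither a maturity condition for the stage-1 count nor a condition for ending the pause, and it uses an undefined word that the other three statements of the rule lack.

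The loss is conditional on when the count is taken. At patient 15's first dose, the stop probability for an inactive drug roughly halves at 1 ACC patient a month and falls further at 2. A 12-week wait recovers much of it, and a 24-week wait all of it. The harm is to early stopping and expected sample size. The sizes rest on 55% failing by 24 weeks, constant hazard and Poisson accrual; the direction does not. The early-leaver figures are secondary, since they need both the less likely reading and assumed rates of 10 to 20%. The change is worth making because the rule as written can give a wrong decision to continue and the correction is short.

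**What to change.** Use one common statement in 4.5, the schema, the Summary and 10.2: ACC enrollment pauses once the 15th ACC patient has received a first dose. The count is made when each of these 15 has completed 24 weeks or stopped treatment, or earlier once the decision can no longer change. At the written cut-off that is the seventh counted failure, or the ninth patient to complete 24 weeks, since at most six failures are then possible. Enrollment stays paused until then. Every dosed patient is included, with or without a re-scan, and *evaluable* is deleted.

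In the same edit, reconcile three things: how withdrawals of consent are counted (4.5 counts any reason for the ACC look; the schema, Summary and 10.2 exclude them); the 12-participant enrollment-stop sentences in 8.1.11 and 8.2.11, which should be reconciled with 4.5 or removed; and the cut-off of 7 with the operating characteristics quoted in 10.2, which correspond to 8.

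The cost is one statement in four places and an ACC accrual pause of up to 24 weeks, shorter if the decision is settled sooner.

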4.6 Concomitant Medications/Treatments

4.6.1 Permitted Medications

All treatments that the investigator considers necessary for a subject's welfare may be administered at the discretion of the investigator in keeping with the community standards of medical care and the protocol's prohibited medications in 4.5.2. All concomitant medication will be recorded on the case report form (CRF) including all prescription, over-the-counter (OTC), herbal supplements, and IV medications and fluids. If changes occur during the trial period, documentation of drug dosage, frequency, route, and date may also be included on the CRF.

Subjects are permitted the use of topical, ocular, intra-articular, intranasal, and inhalational corticosteroids (with minimal systemic absorption). A brief (less than 3 weeks) course of corticosteroids for prophylaxis (e.g., contrast dye allergy) or for treatment of non-autoimmune conditions (e.g., delayed-type hypersensitivity reaction caused by a contact allergen) is permitted.

Inhaled or topical steroids are permitted at any dose in the absence of active autoimmune disease. Adrenal replacement steroid doses are permitted as long as < 10mg prednisone (or equivalent) per day.

Concomitant palliative and supportive care for disease related symptoms (including bisphosphonates and RANK-L inhibitors) is allowed if initiated prior to first dose of study therapy.

All concomitant medications received within 28 days before the first dose of trial treatment and 30 days after the last dose of trial treatment should be recorded. Concomitant medications administered past 30 days of treatment should be recorded if associated with an SAE.

4.6.1.1 Palliative Radiation Therapy or Surgery

Non-target Lesion

During study treatment, palliative radiation therapy or surgery to **non-target lesions** is permitted for symptom control. Study treatment must be held for the duration of the palliative treatment.

Target Lesion

If radiotherapy or surgery is needed for a **target lesion**, the patient is permitted to continue study treatment if another target lesion can be identified. Study treatment must be held for the duration of the palliative treatment. The newly selected target lesion will then be included for future scan assessments. In addition, previous scan assessments will be reevaluated to include the newly selected target lesion. If another target lesion cannot be identified, it will be per physician's discretion if treatment may continue after discussion with the PI and study QAM.

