6.0 ENDPOINT ASSESSMENT

6.1 Definitions

For the purposes of this study, patients should be re-evaluated for response every 12 weeks (± 7 days). In addition to a baseline scan, confirmatory scans should also be obtained 8 weeks following initial documentation of objective response greater than Stable Disease (SD). Tumor assessments for all subjects should continue as per protocol even if dosing is interrupted. Tumor measurements should be made by the same investigator or radiologist for each assessment whenever possible.

Response and progression will be evaluated in this study using the new international criteria proposed by the revised Response Evaluation Criteria in Solid Tumors (RECIST) guideline (version 1.1).⁴⁴ Changes in the largest diameter (unidimensional measurement) of the tumor lesions and the shortest diameter in the case of malignant lymph nodes are used in the RECIST criteria.

High resolution CT with oral/intravenous contrast or contrast-enhanced MRI is the preferred imaging modalities for assessing radiographic tumor response. If a subject has a known allergy to contrast material, please use local prophylaxis standards to obtain the assessment with contrast if at all possible, or use the alternate modality. In cases where contrast is strictly contraindicated, a non-contrast scan will suffice. Screening assessments should be performed within 28 days of registration. Brain MRI is the preferred imaging method for evaluating CNS metastasis, and assessment is only required during screening for patients who have a known history of CNS disease. All known or suspected sites of disease (including CNS if history of CNS metastases) should be assessed at screening and at subsequent assessments using the same imaging method and technique. If more than one method is used at screening, then the most accurate method according to RECIST 1.1 should be used when recording data, and should again be used for all subsequent assessments. Previously treated CNS metastases are not considered measurable lesions for purposes of RECIST determined response. Subjects with a history of brain metastasis should have surveillance MRI approximately every 12 weeks, or sooner if clinically indicated.

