6.2 Primary Endpoint

Median progression-free survival (PFS) as well as PFS at 6 and 12 months [defined the absence of death and of progression of disease. The Response Evaluation Criteria in Solid Tumors (RECIST 1.1) criteria will be used for objective tumor response assessment].⁴⁴

- Clinical and radiological assessments will be performed every 12 weeks (± 7 days) while on treatment. All patients who receive at least one dose of nivolumab and have had their disease re-evaluated will be included in the primary analysis of PFS.

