Target lesions. All measurable lesions up to a maximum of 2 lesions per organ and 5 lesions in total, representative of all involved organs, should be identified as target lesions and recorded and measured at baseline. Target lesions should be selected on the basis of their size (lesions with the longest diameter), be representative of all involved organs, but in addition should be those that lend themselves to reproducible repeated measurements. It may be the case that, on occasion, the largest lesion does not lend itself to reproducible measurement in which circumstance the next largest lesion, which can be measured reproducibly should be selected. A sum of the diameters (longest for non- nodal lesions, short axis for nodal lesions) for all target lesions will be calculated and reported as the baseline sum diameters. If lymph nodes are to be included in the sum, then only the short axis is added into the sum. The baseline sum diameters will be used

NU Study Number: NU 16N03
BMS Study Number: CA 209-802

as reference to further characterize any objective tumor regression in the measurable dimension of the disease.

Non-target lesions. All other lesions (or sites of disease) including any measurable lesions over and above the 5 target lesions should be identified as non-target lesions and should also be recorded at baseline. Measurements of these lesions are not required, but the presence, absence, or in rare cases unequivocal progression of each should be noted throughout follow-up.

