6.6 Response Criteria – RECIST v1.1

6.6.1 Evaluation of target lesions

Complete Response (CR): Disappearance of all target lesions. Any pathological lymph nodes (whether target or non-target) must have reduction in short axis to <10mm.

Partial Response (PR): At least a 30% decrease in the sum of the diameters of target lesions, taking as reference the baseline sum diameters.

Progressive Disease (PD): At least a 20% increase in the sum of the diameters of target lesions, taking as reference the smallest sum on study (this includes the baseline sum if that is the smallest on study). In addition to the relative increase of 20%, the sum must also demonstrate an absolute increase of at least 5 mm (0.5 cm). (Note: the appearance of one or more new lesions is also considered progressions).

Stable Disease (SD): Neither sufficient shrinkage to qualify for PR nor sufficient increase to qualify for PD, taking as reference the smallest sum diameters while on study.

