10.0 STATISTICAL CONSIDERATIONS

10.1 Study Design/Study Endpoints

This is a single arm open label phase II clinical trial which will assess the anti-tumor efficacy of nivolumab in combination with ipilimumab in ACC. As these two monoclonal anti-bodies already have been studied and approved as monotherapy or combination in other histological tumor types we believe that a phase II study is appropriate for development of these drugs in metastatic/recurrent adenoid cystic carcinoma (ACC). The non-adenoid cystic carcinomas (non-ACC) of major or minor salivary glands are for exploratory purposes for signal finding and will not be included in our statistical plan.

10.1.1 Primary:

To assess the median progression-free survival (PFS) as well as PFS at 6 and 12 months [defined as the absence of death and of progression of disease] in patients with metastatic/recurrent and progressive ACC. The Response Evaluation Criteria in Solid Tumors (RECIST 1.1) criteria will be used for objective tumor response assessment

10.1.2 Secondary:

- (1) To assess the efficacy of nivolumab and ipilimumab according to response rate (RR), disease control rate (DCR; CR, PR, and SD at 24 weeks), overall survival (OS) and progression free survival (PFS) in the above population using RECIST criteria.
- (2) To assess the efficacy of nivolumab and ipilimumab according to ORR, DCR, PFS, and OS in the above population using irRECIST criteria.
- (3) To assess the safety and tolerability profile of nivolumab and ipilimumab therapy in the above population using CTCAE version 4.03
- (4) To assess the immune-related biomarkers and their association with treatment response
- (5) Assess activity of nivolumab and ipilimumab in non-ACC malignant salivary gland tumors (MSGTs)

10.1.3 Exploratory endpoints:

- To assess the predictive value of baseline immunosuppressive biomarker PD-L1 protein on tumor cells and the expression level and localization of

NU Study Number: NU 16N03
BMS Study Number: CA 209-802

other markers of inflammatory/immune signature. Correlations between cell free tumor DNA and tumor tissue genomic aberrations with anti-tumor efficacy of nivolumab/ipilimumab combination will be explored.

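### Replacing a locally treated target lesion and re-reading earlier scans can change a progression already recorded, and no rule protects that date in the primary PFS analysis

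*Combined protocol and SAP*

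**What the plan says.** Section 4.6.1.1 covers radiotherapy or surgery to a target lesion during study treatment: "the patient is permitted to continue study treatment if another target lesion can be identified". The new lesion is used on later scans, and "previous scan assessments will be reevaluated to include the newly selected target lesion". The section does not say whether the treated lesion leaves the earlier sums, which baseline and nadir then apply, or whether a progression already recorded stands.

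Section 6.5 says that measurable lesions, up to two per organ and five in total, "should be identified as target lesions and recorded and measured at baseline". Section 6.6.1 defines progression as "At least a 20% increase in the sum of the diameters of target lesions", measured from the smallest sum on study, with an absolute increase of at least 5 mm. New lesions also count as progression, as does unequivocal non-target progression (6.6.2).

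The primary endpoint (6.2) is "Median progression-free survival (PFS) as well as PFS at 6 and 12 months". Section 10.1 states: "This is a single arm open label phase II clinical trial". On who reads the scans, 6.1 says: "Tumor measurements should be made by the same investigator or radiologist for each assessment whenever possible". The only later review, in 6.6.2, concerns non-target progression and may be done by the principal investigator. Sections 6.2, 6.3 and 10.3 give no event, censoring or sensitivity rule for local treatment of a target lesion.

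**The concern.** Changing the lesion set after baseline changes the baseline sum, the nadir and every earlier percentage change. Sections 6.5 and 6.6.1 assume that none of these move. Section 4.4 allows treatment to continue after an initial progression. A patient can therefore have progression recorded, stay on treatment, have a target lesion irradiated or resected, and then have the earlier scans re-read with a different set of lesions. Nothing in the documents says which reading gives the PFS date.

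The replacement is chosen after the course of disease has been seen, by readers for whom no blinding or independent review is described, and there is no control arm in which the same practice would operate. Primary PFS depends directly on these reads. The final count in Section 10.2 (24 or fewer of 43 with stable disease or better rejects the regimen) draws on the same assessments.

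**Working it through.** **1. Can a re-read change a recorded progression?** The lesion sizes here are assumed; the 20% and 5 mm thresholds come from 6.6.1.

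- As first read: A 30→40 mm and B 20→22 mm. Sum 50→62 mm; 12/50 = +24%, +12 mm. Progression.
- A replaced by C (20→21 mm): sum of B and C 40→43 mm; 3/40 = +7.5%, +3 mm. Stable.
- A kept and C added: sum 70→83 mm; 13/70 = +18.6%, +13 mm. Stable, because the 20% threshold is missed.

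So the recorded progression can be lost whether or not the treated lesion leaves the earlier sums.

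**2. Can it go the other way?** Yes. Take lesions of 30→33 mm and 20→20 mm: sum 50→53 mm, 3/50 = +6%, stable. Replace the first with a lesion of 15→23 mm: sum 35→43 mm, 8/35 = +22.9%, +8 mm, progression.

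**3. Reproduce the plan's design figures (10.2).** Inputs: p0 = 0.45, p1 = 0.65, 15 patients in stage 1, 43 in total, reject at 24 or fewer. Let r be the largest number of stage 1 successes at which the trial stops.

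- Early termination = P(Bin(15, p) ≤ r)
- E(N) = 15 + (1 − early termination) × 28
- P(declare effective) = Σ over x from r+1 to 15 of P(Bin(15, p) = x) × P(Bin(28, p) ≥ 25 − x)

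With r = 7 and p = 0.45, early termination is 0.6535, E(N) = 15 + 0.3465 × 28 = 24.70 and the false-positive probability is 0.0481. At p = 0.65 power is 0.8035. These match the stated 0.654, 24.70, 0.048 and 0.196.

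The written stage 1 rule stops at 7 or more withdrawals of 15, that is, at 8 or fewer successes (r = 8). The false-positive probability is then 0.0367.

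**4. Illustration only: k of 43 calls reversed from failure to success.** The value of k is an assumption. One patient is 1/43 = 2.3 percentage points.

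Calculation (a) uses r = 7 and raises the apparent rate to 0.45 + k/43 in both stages. Calculation (b) uses r = 8, leaves stage 1 untouched and adds k to the final count, so 25 − k true successes suffice.

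| k | apparent rate in (a) | (a) | (b) |
|---|---|---|---|
| 0 | 0.450 | 0.048 | 0.037 |
| 1 | 0.473 | 0.086 | 0.058 |
| 2 | 0.497 | 0.143 | 0.082 |
| 3 | 0.520 | 0.220 | 0.108 |

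With the rates rounded to 0.47, 0.50 and 0.52, (a) gives 0.080, 0.153 and 0.221. Calculation (b) is closer to the written text, because stage 1 counts withdrawals before 24 weeks rather than RECIST progression.

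**The case against.** A reader might infer that the rule can only delay or remove progression, so that PFS must be biased upward. The documents do not support that. Step 2 shows a re-read creating progression. Replacement also has a legitimate purpose: if an irradiated or resected lesion stayed in the sum, its shrinkage would count as tumour reduction and could mask growth elsewhere.

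Nor does the text say that the treated lesion is removed from earlier sums or that a recorded date is altered. Both are inferred from silence. The replacement does not decide PFS alone: other target lesions stay in the sum, and new-lesion or non-target progression survives any swap. If 6.5 was followed, a replacement that was measurable at baseline exists only where a patient exceeded the limits of two per organ or five in total. A reversal therefore needs progression by target sum alone, local treatment of a target lesion, an available replacement and a re-read that overturns the call. That may be rare, and zero cases is compatible with the documents.

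The final count is also loosely tied to PFS. Section 10.2 gives no time point for stable disease or better, so a patient stable at the first scan may already count, whatever happens later.

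All of this stands as a limit on direction and size. It does not remove the conflict between 4.6.1.1 and 6.5–6.6, or supply the missing rule on which reading gives the PFS date.

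**Conclusion.** The point holds as a gap in the definition of the primary endpoint. The swap and the re-read are explicit, they conflict with a lesion set fixed at baseline, and a progression recorded from the target-lesion sum can be changed afterwards. Longer PFS is the more likely direction. That is a judgement, resting on the treated lesion tending to be a growing or symptomatic one and on its replacement being picked with its course known.

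The size is unknown. The ranges 0.086–0.220 (from 0.048) and 0.058–0.108 (from 0.037) show only how sensitive the decision rule would be to one to three reversed calls. They are not estimates of the trial's actual error rate, and they assume that each reversal changes the patient's status in the count. The correction is worth making because it is cheap and makes the PFS date reproducible.

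**What to change.** - Reconcile 4.6.1.1 with 6.5–6.6. Say whether the treated lesion stays in earlier sums, which baseline and nadir apply after a replacement, and whether a re-read may introduce an earlier progression.
- State in 4.6.1.1 and 10.3 that a RECIST 1.1 progression date recorded before the local procedure is not changed by any re-read, for the primary PFS analysis or for the count against 24 of 43.
- Add to 10.3 a sensitivity analysis of PFS and of the count in which radiotherapy or surgery to a target lesion is an event on its date. Give censoring of PFS at that date as the alternative. The event version should be a sensitivity analysis only, because 6.3 defines PFS by progression or death and symptom control alone is neither.

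Permission for palliative treatment does not change. The cost is some protocol wording and one extra analysis, using the procedure dates and the reads as first recorded. The sensitivity result may be less favourable than the main one.
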